## 7.3 Immunogenicity Assessments

Blood samples for the assessment of immunogenicity will be collected as specified in the [SCHEDULE OF ACTIVITIES](#) and in the table below (Table 4).

**Table 4: Blood Volume Needed for Immunogenicity Analysis**

Assessments	Randomization 	2 weeks	4 weeks	8 weeks	12 weeks	14 weeks	16 weeks	20 weeks	24 weeks	26 weeks	28 weeks	32 weeks	36 weeks
	Volume Collected (mL)												
Anti-drug antibody (ADA) 	15	10	10	10	10	10	10	10	10	10	10	10	10
Neutralizing Antibody (NAb) 	5	5	5	5	5	5	5	5	5	5	5	5	5
Anti-HCP Antibody 	5	5	5	5	5	5	5	5	5	5	5	5	5
Drug	6	6	6	6	6	6	6	6	6	6	6	6	6

Assessments	Randomization 	2 weeks	4 weeks	8 weeks	12 weeks	14 weeks	16 weeks	20 weeks	24 weeks	26 weeks	28 weeks	32 weeks	36 weeks
Volume Collected (mL)													
concentration 													

Blood samples will be drawn into serum separator tubes (SST).

Blood samples will be drawn into K2EDTA plasma tubes.

Results of the samples collected as part of MYL-GAI-3001 trial will be used.

The clinical laboratory will provide specific sample kits to the Investigator site prior to the visit of patients. Instructions for collecting, handling, storing and shipping of clinical samples will be provided in the laboratory manuals. Samples and lab results collected at randomization will be considered as baseline.

The central laboratories are:

Samples from Europe will be sent to	Q  (Squared) Solutions [name] UK
Samples from US will be sent to	Q  (Squared) Solutions [name] USA

The site must store the immunogenicity and drug concentration samples at -20°C ± 5°C or lower and ship the samples in batches on a monthly basis to the central laboratory where they will be stored at -80 ± 5°C or below. Primary and backup samples should not be sent in the same shipment. Both immunogenicity and drug concentration samples must be shipped frozen on dry ice. Temperature monitoring devices (e.g. Temp Tale®) must be included in all sample shipments.

### **7.3.1. Anti-Drug Antibody**

Two conventional radioimmunoassays (RIA) were employed for the assessment of anti-drug antibodies (ADA). A two assay approach, applied in a blinded fashion, was utilized due to the potential structural differences between drug products arising from the different host cells used in production. The two assays were identical except for the use of a unique tracer: I-Lantus, designated for the ‘LAN assay’, and I-MYL IG, designated as the ‘MIG assay’. In both assays samples underwent a pre-treatment step that

included acid dissociation to release any anti-insulin antibodies complexed with free drug, followed by charcoal adsorption of the free insulin analog. The treated samples were then incubated with a fixed amount of each tracer under the following conditions:

- Assay buffer only (no inhibitor)
- Assay buffer containing excess unlabeled MYL IG
- Assay buffer containing excess unlabeled Lantus
- Assay buffer containing excess unlabeled Human Insulin

ADA complex formation with the tracers is measured via gamma counting and expressed as a percentage of bound to total radioactivity (%B/T).

In keeping with the multi-tiered sample analysis recommendations for immunogenicity testing from published white papers (12, 13), and current regulatory guidance (14), the assay design employed a screening tier (no inhibition), confirmatory tier (competitive inhibition with excess drug), and characterization tier (competitive inhibition with excess human insulin) that were assessed simultaneously. Since inhibition with excess drug and human insulin were included within the assessment of each sample, the total anti-drug antibody and insulin cross reactivity results were reported in terms of percent specific binding (%SB), which is the difference between the %B/T for the uninhibited and the inhibited samples for each assay. Analogous to titer values, the %SB is the relative amount of antibody present in the samples. Cut-points for these assessments were determined based on %SB during assay validation and applied during sample analysis for scoring total and cross reactive ADA positive samples:

Assay	Assessment	Assessment Definition
MIG	Total ADA	%B/T (no inhibitor) - %B/T (excess MYL IG)
	Cross-reactive ADA	%B/T (no inhibitor) - %B/T (excess human insulin)
LAN	Total ADA	%B/T (no inhibitor) - %B/T (excess LAN)
	Cross-reactive ADA	%B/T (no inhibitor) - %B/T (excess human insulin)

In addition, drug-specific ADA was assessed by determining the %B/T difference between samples inhibited with excess Lantus and MYL IG in each assay:

Assay	Assessment	Assessment Definition
MIG	Drug specific ADA	%B/T (excess LAN) - %B/T (excess MYL IG)
LAN	Drug specific ADA	%B/T (excess MYL IG) - %B/T (excess LAN)

For this assessment no cut-point was determined or applied, and the results are reported as %B/T.

Drug concentration samples were obtained to support an alternative format for immunogenicity testing (bridging ELISA). With the use of a RIPA format, drug concentration testing is not required.

Assessment of total antibody positive samples for the presence of neutralizing antibodies will be conducted at the discretion of the clinical team.

### ***7.3.2. Antibodies against Host Cell Protein Antibodies (anti-HCP)***

The multi-tiered sample analysis approach for immunogenicity testing will also be employed for the detection of antibodies directed against host cell proteins present in the drug product. In keeping with the multi-tiered sample analysis recommendations for immunogenicity testing, the assay design employed screening (no inhibition), confirmatory (competitive inhibition with excess HCP), and titer tiers. However, since a high positive rate of pre-existing antibodies is anticipated due to ubiquitous exposure of the general population to yeast proteins, sample analysis is limited to the screening and confirmatory tiers. Relative anti-HCP antibody levels over time will be estimated using sample ECL response in the screening assay.

The assay employed for anti-HCP antibody evaluation will be fully validated using a surrogate positive control antibody, developed from host cell protein antigens (*Pichia pastoris*). Host antigens for the reference product (from the host *Escherichia coli* K12) are not available to develop a parallel assay for Lantus anti-HCP antibodies. In order to maintain blinded analysis, both treatment arms will be evaluated with the assay. Any change in the sample analysis method will be mentioned in the sample analysis plan.

## **7.4 Safety Assessments**

### ***7.4.1. Medical History***

Medical history will be recorded at randomization and must include any clinically relevant prior diagnosis, concomitant diseases and abnormalities, documentation of drug allergies, prior systemic and local allergic reactions to insulin. The medical history should be checked against the inclusion and exclusion criteria.

### ***7.4.2. Prior and Concomitant Medication***

All treatments being taken by the patients at the time of randomization and all treatments given in addition to the trial treatment (investigational products), are regarded as concomitant treatments and must be documented in the eCRF.

During the extension study the Investigator should ensure that no medications listed in [Table 2](#) are initiated.

### ***7.4.3. Vital Signs***

Vital signs are body temperature, respiratory rate, sitting pulse, and blood pressure (both systolic and diastolic). The patient should be resting in sitting position for at least 5 minutes before the measurements are performed. The vital signs will be recorded as specified in the [SCHEDULE OF ACTIVITIES](#).

### ***7.4.4. Physical Examination***

Complete physical examination data will be recorded as specified in the [SCHEDULE OF ACTIVITIES](#) and will include the following assessments: general appearance, head, ears, eyes, nose and throat (including thyroid), skin, respiratory system, cardiovascular system, abdomen, lymph nodes, musculoskeletal system, gastrointestinal system (including mouth) and neurological system; and a diabetic foot examination.

### ***7.4.5. Electrocardiogram***

A 12-lead ECG will be done as specified in the [SCHEDULE OF ACTIVITIES](#). The ECG will be performed in supine position after at least 5 minutes resting in the supine position. The results will be assessed qualitatively as normal or as abnormal with the abnormalities specified.

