**SCHEDULE OF ACTIVITIES**

	Visits													
	V1	V2	V3	V4	V5	V6	V7	V8	V9	V10	V11	V12	V13  (EOT)	V14  (FU)
Extension Study Week	0	2	4	8	12	14	16	20	24	26	28	32	36	40
Extension Study Day	0	14±3	28±3	56±3	84±3	98±7	112±7	140±7	168±7	182±7	196±7	224±7	252±7	280±7
Informed Consent 	x													
Inclusion/Exclusion Criteria Review	x													
Previous and current insulin usage history	√													
Dilated Ophthalmoscopy / Retinal photography testing 	x	x	x											
Standard-of-care specifics 	x	x	x	x	x	x	x	x	x	x	x	x	x	
Age, Gender, Race	x													
Body Weight, Height and BMI 	√												x	
Pregnancy Test 	√	x	x	x	x	x	x	x	x	x	x	x	x	
Medical History and Concomitant Illness	x													
Concomitant Medications	x	x	x	x	x	x	x	x	x	x	x	x	x	
Vitals signs measurement (sitting)	√	x	x	x	x	x	x	x	x	x	x	x	x	
Physical examination	√	x			x	x			x	x			x	
12-lead ECG (supine)	√				x	x			x	x			x	
Fresh Randomization with capture of old randomization number 	x													
Record AEs and SAEs, local and systemic allergic reactions and hypoglycemic events 	x	x	x	x	x	x	x	x	x	x	x	x	x	x 
Record device safety information (disposable needle or pen)		x	x	x	x	x	x	x	x	x	x	x	x	
Fasting Plasma Glucose	√			x	x			x	x				x	
HbA1c Assay	√				x				x				x	
HIV, HBsAg, and HCVAb	√													
Sampling for hematology, blood chemistry and urinalysis 	√				x				x				x	
Fasting lipid profile	√				x				x				x	
Sampling for immunogenicity	√	x	x	x	x	x	x	x	x	x	x	x	x	
Review 8-point SMBG Profile performed in the week before the visit 	√	x	x	x	x	x	x	x	x	x	x	x	x	
Dose review of Mylan's insulin glargine/Lantus® and insulin lispro and instruction	x	x	x	x	x	x	x	x	x	x	x	x		
Dispense Trial Medication and ancillary supplies	x		x	x	x		x	x	x		x	x		

	Visits													
	V1	V2	V3	V4	V5	V6	V7	V8	V9	V10	V11	V12	V13  (EOT)	V14  (FU)
Extension Study Week	0	2	4	8	12	14	16	20	24	26	28	32	36	40

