#### ***9.9.7. ECG***

Summary of frequency table of percentage of patients in categories such as abnormal/non-clinically significant and abnormal/clinically significant will be presented by visit and sequence group.

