17.3. ECG EVALUATIONS

Results from the central ECG (Electrocardiogram) Reading Centre will be included in the reporting of this study.

Week 52 result from MYL-GAI-3001 trial will be considered as baseline.

Frequency and percentage of overall assessment of ECG (investigator's judgment) will be presented.

The percentage of patients in categories such as abnormal/non-clinically significant and abnormal/clinically significant will be summarized and treatment sequence group comparison will be performed using Fisher's exact test. The p-value will be presented for the same.

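### SAP 17.3 names the week-52 ECG as baseline but no planned ECG comparison uses it, so long-standing and new abnormalities count alike; the same section also leaves the source of the reading unclear

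*Protocol*

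**What the plan says.** Protocol 7.4.5 describes a qualitative reading: "The results will be assessed qualitatively as normal or as abnormal with the abnormalities specified". In the Schedule of Activities the week-0 ECG is carried over from MYL-GAI-3001, and new ECGs are taken at weeks 12, 14, 24, 26 and 36. Protocol 9.9.7 plans one frequency table, of abnormal/non-clinically significant (NCS) and abnormal/clinically significant (CS), which "will be presented by visit and sequence group".

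SAP 17.3 contains four statements:

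- Source: "Results from the central ECG (Electrocardiogram) Reading Centre will be included in the reporting of this study".
- Baseline: "Week 52 result from MYL-GAI-3001 trial will be considered as baseline".
- Summary: "Frequency and percentage of overall assessment of ECG (investigator's judgment) will be presented".
- Test, by the Fisher exact method: "The percentage of patients in categories such as abnormal/non-clinically significant and abnormal/clinically significant will be summarized and treatment sequence group comparison will be performed".

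Elsewhere the SAP does use baseline for safety data. Section 17.2 plans shift-from-baseline tables for laboratory results, and most of the vital-sign criteria in 17.4.1 include a change from baseline.

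**The concern.** The trial asks whether switching between the two glargines changes safety compared with staying on Lantus. For ECG that is a question about change within a patient, and the schedule suits it: a pre-randomization tracing is in hand, and later ones fall at the end of each period and two weeks after the week-12 and week-24 transitions.

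The planned comparison asks something else, namely what share of patients sit in each abnormal category. Patients abnormal before randomization add the same noise to both groups and dilute any difference in new findings. The baseline is declared, but nothing in 17.3 refers to it again.

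The section also does not settle whose reading is analysed. It opens with a central reading centre and then tabulates the investigator's judgment. If the week-52 ECG came from one reader and later ECGs from another, a difference between readers could pass for a change in the patient.

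**Working it through.** **Is baseline used?** Going through the ECG outputs one by one:

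| Output | Uses week 52 as comparator? |
|---|---|
| Protocol 9.9.7, frequency table by visit | No |
| SAP 17.3, frequency of overall assessment | No |
| SAP 17.3, Fisher's exact test on abnormal/NCS and abnormal/CS | No |

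There is no shift table, no category for new or worsened findings, no baseline adjustment and no restriction to patients normal at baseline.

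**The plan's own figure.** None exists for ECG. The only design figure is 90% power for HbA1c equivalence (protocol 9.1), and it supplies the group size used below. With 10% not evaluable, n = 69 × 0.9 ≈ 62 per group. The standard error is 0.61 × √(2/62) = 0.1096, and 0.4/0.1096 − 1.96 = 1.69, so power = 2Φ(1.69) − 1 ≈ 91%. The stated 90% reproduces. It has no bearing on ECG beyond giving n; the ECG analysis uses the safety population, which could be nearer 69 per group.

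**Illustrative cost of ignoring baseline.** Every ECG rate here is an assumption. Let b be the proportion abnormal at week 52, assume those abnormalities persist, and let r be the rate of new abnormality among patients normal at baseline.

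- Visit prevalence: p = b + (1 − b) × r, tested on 62 per group.
- New onset: r itself, tested on 62 × (1 − b) per group, rounded.
- Power: exact enumeration of Fisher's exact test at two-sided 0.05.

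Example at b = 0.20 with r = 15% v 2%: prevalence is 0.20 + 0.80 × 0.15 = 32.0% against 0.20 + 0.80 × 0.02 = 21.6%. New onset is tested on 62 × 0.80 ≈ 50 per group.

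| Abnormal at baseline | Prevalence compared | Power, visit prevalence | Patients per group, new onset | Power, new onset |
|---|---|---|---|---|
| 0% | 15.0% v 2.0% | 66% | 62 | 66% |
| 10% | 23.5% v 11.8% | 32% | 56 | 59% |
| 20% | 32.0% v 21.6% | 20% | 50 | 51% |
| 35% | 44.8% v 36.3% | 13% | 40 | 36% |

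With r = 5% v 2%, both analyses have under 5% power at every baseline rate tried from 0% to 50%, and new onset does no better than prevalence.

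Two limits apply. The calculation pools the two abnormal categories, whereas the SAP keeps them apart. It also covers new onset among baseline-normal patients only, so it approximates a test on new or worsened category.

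**Whose reading?** Protocol 7.4.5 names no reader. Protocol 7.1 describes central facilities for laboratory samples, and no central ECG reading appears in the protocol text available for this review, from which some pages were missing. SAP 3.3, which lists changes from the protocol, does not mention one. The conflict inside SAP 17.3 does not depend on the missing pages.

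**The case against.** The strongest reply is that new ECG findings are already caught elsewhere. Protocol 8.5 names ECG and has clinically significant findings recorded as adverse events when they appear after dosing, or were present at baseline and worsen. SAP 17.1 then compares treatment-emergent events between sequence groups by Fisher's exact test in each period. This stands: a reader might infer that new abnormalities go undetected, and for clinically significant ones that is wrong. What remains is change that is not clinically significant, which is one of the two categories SAP 17.3 tests, and the fact that the ECG test does not measure change.

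A reader might also infer that pre-existing abnormalities swamp new ones. The documents give no ECG abnormality rate, SAP Appendix 2 lists ECG among the selection criteria, and clinically significant abnormalities at baseline may be few. The loss is nil at 0% and can be called only a possible loss of sensitivity. Nor is there bias between the groups, because randomization balances pre-existing abnormalities on average.

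It can also be said that SAP section 8 breaks descriptive summaries down by visit, so baseline frequencies may be shown beside later ones, that SAP 6.3 mentions shift tables in general terms, and that table templates are kept separately. Group frequencies side by side still do not show which patients changed, and 17.3 commits to no ECG shift table.

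On the reader, one might conclude that the central reading centre is an error and should be struck out in favour of the investigator. The documents do not support that. Protocol 7.4.5 is silent on the reader, a central reading and an investigator's judgment of significance can coexist, and protocol 3.5 leaves investigators unblinded.

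Finally, the absence of the CS/NCS split from 7.4.5 is not a real contradiction: protocol 8.5 has the investigator judge clinical significance and 9.9.7 names those categories.

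**Conclusion.** The point holds as a minor one. SAP 17.3 defines a baseline that none of its ECG comparisons uses, so the planned test is less sensitive to change after a switch than the data allow. If 10% to 35% of patients were abnormal at week 52 and new abnormality ran at 15% v 2%, power would be roughly a third to a half of what a new-onset comparison gives (32% v 59% at 10%; 13% v 36% at 35%). Those rates are assumptions. With no abnormal baseline ECGs there is no loss, and for a difference as small as 5% v 2% neither analysis is useful at this sample size. The randomized comparison is not biased, and clinically significant new or worsened findings have a second route through adverse events.

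The unclear source of the reading is a separate, textual defect within SAP 17.3 and rests on no assumption. The documents show that it must be resolved, not which way.

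**What to change.** In SAP 17.3:

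1. Add a shift table by sequence group (normal, abnormal/NCS, abnormal/CS) from the week-52 ECG to each scheduled visit and to the worst post-baseline reading.
2. Make the Fisher comparison on patients whose category is new or worse than at week 52, and state the denominator. The plain frequencies can stay as description.
3. State whether the analysed result is the central reading or the investigator's judgment, and use that one source for both the baseline and the post-baseline readings. If both are kept, say which feeds the test.

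Items 1 and 2 cost SAP wording and one further table from tracings already scheduled or held, with no new assessments. Item 3 needs the sponsor to confirm which readings exist for week 52 as well as for the extension visits. If the two sets come from different readers, the shift table needs that caveat or a consistent re-reading, and the latter would be an added cost.

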#### ***7.4.6. Local and Systemic Allergic Reactions***

Local and systemic allergic reactions will be recorded as specified in the [SCHEDULE OF ACTIVITIES](#). The Investigator should ask the patient at each trial visit about allergic reactions and check the injection site(s) for possible local allergic reactions.

If a patient develops any type of allergic reaction, routine evaluations for identifying the cause and type of allergic reaction need to be done. These may include skin biopsy, blood sample collection for further testing, skin tests for detecting allergens or other standard methods considered essential by the Investigator.

#### ***7.4.7. Adverse Events and Serious Adverse Events***

Adverse events and SAEs will be recorded as specified in the [SCHEDULE OF ACTIVITIES](#) from the time of signing the informed consent form until the end of the follow-up visit. After the follow-up visit, any SAEs reported by the patients will be recorded if they are deemed related to trial drugs by the Investigator.

#### ***7.4.8. Hypoglycemic Events***

Patients will be instructed to record all hypoglycemic events in the patient diary from week 0 through the EOT visit. The hypoglycemic events will be reviewed by the Investigator and transcribed into the eCRF by the Investigator or designee after the diary has been collected. Details of the different types of hypoglycemic events are provided in section [7.5.6.1](#). Severe and serious hypoglycemic episodes will be reported to the sponsor immediately, according to section [8.3.2.8](#).

#### ***7.4.9. Safety Related to Device Use***

Adverse events could potentially result from device failure or user error. These safety issues will be identified, documented, investigated and if appropriate, reported. Any SAE associated with a device issue will be reported to the sponsor immediately according to section [8.3.2.8](#).

##### **7.4.9.1. Adverse Events Associated with Device and Device Complaints**

All AEs associated with the device will be captured according to section [8.3](#), including an assessment of causality by the Investigator. Any device-related complaints will be investigated at the discretion of the sponsor.

#### **7.4.9.2. Investigator's Responsibility**

- During enrollment, patients will be instructed to document in their diary and inform the Investigator (during the next scheduled visit) about any difficulties encountered during the administration of the drug.
- Patients will be instructed to immediately report to the Investigator any suspected failure of the device to deliver the intended dose, or an SAE associated with the device.
- For AEs associated with use of the device, the Investigator will record the AE term in the eCRF to capture both the adverse consequence as well as the association with the device (e.g. injection site pain from accidental needle stick).
- The Investigator will record in the eCRF whether or not the device issue resulted in an AE; an assessment of whether the AE was related to the drug, the device, or both; and any other relevant information about the patient's condition.
- Any device-related complaint resulting in an SAE will be reported to Mylan within 24 hours (per section 8.3.2.8).
- Even in the absence of a report by the patient of device failure or a device related AE, if the Investigator sees that the pen is broken/damaged or disassembled, the Investigator will replace the device and send the damaged device to the CRO/Mylan.

#### **7.4.9.3. Sponsor's Responsibility**

- For SAEs, Mylan will independently evaluate whether the SAE was drug-related or related to an adverse device effect.
- In the event that the information available in the eCRF is inadequate for root cause analysis, Mylan will send a questionnaire to the Investigator, asking for more details.
- All SAEs related to the use of the needle, which is a legally marketed device, will be recorded and reported to Mylan for investigation and reporting to the needle manufacturer, if deemed necessary, based on the outcome of the investigation.
- Information regarding the circumstances, evaluation, investigation and analysis of all device deficiencies will be included in the clinical study report (CSR).

